## 5.7. Population to be Studied

Patients with MS and impaired walking who completed treatment in Study ADS-AMT-MS301 will be enrolled into the study.

## **6. TRIAL OBJECTIVES AND PURPOSE**

### **6.1. Primary Objective**

- To evaluate the safety and tolerability of ADS-5102 in subjects with MS and walking impairment.

### **6.2. Secondary Objectives**

- To characterize the efficacy of ADS-5102 in subjects with MS and walking impairment as measured by the T25FW (feet/second) at Week 52.
- To characterize the efficacy of ADS-5102 in subjects with MS and walking impairment as measured by the Timed Up and Go (TUG) test, the 2 Minute Walk Test (2MWT), and the Multiple Sclerosis Walking Scale-12 (MSWS-12) at Week 52.
- To characterize the efficacy of ADS-5102 in subjects with MS and walking impairment as measured by the T25FW, the TUG test, the 2MWT, and the MSWS-12 at Weeks 12 and 24, and across all three time points (Weeks 12, 24 and 52).

## 7. INVESTIGATIONAL PLAN

### 7.1. Overall Study Design

This is a multicenter, open-label study of ADS-5102 (amantadine) extended release capsules in subjects with MS and walking impairment who completed study drug treatment for 16 weeks and completed a Week 16 visit in Study ADS-AMT-MS301.

Eligibility for inclusion in this study will require all subjects to be willing to abstain from prohibited medications.

All enrolled subjects will receive ADS-5102 at 137 mg for the first week, 205.5 mg for the second week, and 274 mg for the remainder of the 52-week open-label treatment period.

Subjects will return to the clinic for safety and efficacy assessments at Weeks 4, 12, 24, and 52. In addition, a telephone visit for safety assessments will be conducted at Week 2 and Week 38. Subjects who withdraw from the study prior to completion of the Week 52 visit will have an early termination (ET) visit that includes safety and efficacy assessments. Subjects who complete 52 weeks of open-label treatment will have a final visit for post-treatment safety follow-up and efficacy assessment at 54 weeks, 2 weeks after their Week 52 visit. The end of study (EOS) is defined as when a subject completes the safety follow-up or ET visit.

All study visits and efficacy assessments should be scheduled to occur at approximately the same time of day for each individual subject. Each subject's efficacy assessment should be performed by the same clinical rater, if possible.

Adverse events (AEs) and concomitant medications will be recorded beginning with the first dose of study drug and continuing through the last study visit.

### 7.2. Number of Subjects

Up to approximately 540 subjects will be eligible for enrollment.

### 7.3. Treatment Assignment

In this OLE study, all consented subjects will be treated with ADS-5102 at 274 mg/d following a two-week forced titration period.

### 7.4. Dose Adjustment Criteria

#### 7.4.1. Dose Adjustment for Renal Impairment

Subjects whose estimated glomerular filtration rate (eGFR) falls below 60 mL/min/1.73 m^2, confirmed by repeat testing, should discontinue study drug (see [Section 8.5](#)).

#### 7.4.2. Dose Adjustment for Adverse Events

Study drug may only be withheld for the evaluation or treatment of an adverse event (AE). If, in the judgement of the investigator, study drug should be withheld for the evaluation or treatment of an AE, the investigator may have the subject do so for up to 3 consecutive days, and is then to have the subject resume dosing at the same dose level. If, in the judgement of the investigator, study drug needs to be withheld for more than 3 consecutive days, the investigator must contact

one of the study's Medical Monitors to determine whether drug may be withheld for a longer period or the subject should be permanently discontinued from study drug. This procedure applies to the withholding of study drug throughout the study with the exception of the titration phase.

If study drug is withheld for the evaluation or treatment of an AE occurring during the titration phase (ie, Week 0 to Week 2), the investigator may have the subject stop dosing for up to 3 consecutive days, and then have the subject resume dosing at the same dose level. The subject is to finish the remaining capsules in the blister pack, ie, including the 2-dose overage. Provision must be made for the subject to come to the clinic to be resupplied with study drug without missing any additional doses.

After Week 12, down titration from 274 mg to 137 mg due to adverse events may be considered after consultation with the Medical Monitor.

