## 5. INTRODUCTION

This is an open-label extension (OLE) study for subjects who complete 16 weeks of study drug treatment and a Week 16 visit in Study ADS-AMT-MS301, “A 3-Arm, Multicenter, Double-Blind, Placebo-Controlled, Randomized Study to Assess the Efficacy and Safety of ADS-5102 Amantadine Extended Release Capsules in Multiple Sclerosis Patients with Walking Impairment.” The primary purpose of this study is to extend the evaluation of the safety and tolerability of ADS-5102, an extended-release (ER) capsule formulation of amantadine administered at 274 mg/d, in subjects with multiple sclerosis (MS) and walking impairment from 12 weeks, as in Study ADS-AMT-MS301, to 52 weeks or 64 weeks (including the duration of ADS-AMT-MS301). Additionally, this study is intended to provide supportive evidence of the efficacy of ADS-5102 as a treatment for walking impairment in MS (by way of treating the former ADS-AMT-MS301 placebo subjects), as well as an assessment of the durability of efficacy up to 64 weeks.

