### 9.3. Study Drug Storage

All study drugs must be stored at 25°C (77°F) with excursions permitted to 15-30°C (59-86°F) in a secured location with access limited to authorized personnel.

An authorized pharmacist or designated staff member will dispense the study drug. The dispensing and administration will be recorded in a drug accountability log.

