#### **13.1.1. Adverse Event (AE) Definition**

Any medical condition or clinically significant laboratory abnormality with an onset date before the first date of study drug administration is usually considered to be pre-existing, and should not be documented in the CRF as an AE.

An AE **does** include:

- an exacerbation of a pre-existing illness;
- an increase in frequency or intensity of a pre-existing episodic event or condition;
- a condition detected or diagnosed after study drug administration even though it may have been present prior to the start of the study;
- persistent disease or symptoms present at baseline which worsen following the start of the study.

An AE **does not** include:

- medical or surgical procedures (eg, surgery, endoscopy, tooth extraction, transfusion)  
Note: in this case, the condition that led to the procedure is an AE;
- pre-existing diseases or conditions present or detected prior to start of study drug administration, which do not worsen;
- the disease or disorder being studied or a sign or symptom associated with that disease (ie, signs or symptoms associated with lack of efficacy will generally be considered to reflect underlying disease, rather than AEs, and are considered anticipated);
  - In this study, walking ability is an efficacy parameter and changes in this measure (both positive and negative) will be reported as efficacy outcomes. Worsening of other MS-associated parameters should be reported as AEs
- situations where an untoward medical occurrence has not occurred (eg, hospitalization for elective surgery, elective abortion, social, and/or convenience admissions);
- overdose of either study drug or concomitant medication without any signs or symptoms. (Dosing details will be recorded on the appropriate eCRF(s)).
- pregnancy - Pregnancy in itself is not regarded as an AE unless there is a suspicion that an investigational product may have interfered with the effectiveness of a contraceptive medication (see [Section 13.3.3](#)).

All AEs must be fully and completely documented on the AE page of the CRF and in the subject's medical notes. The following attributes must be assigned: description of AE, dates and times of onset and resolution (or whether ongoing), severity ([Section 13.1.6](#)), relationship to study drug ([Section 13.1.7](#)), whether an SAE or not (Section 13.1.2, and action taken (ie, no action taken; study drug interrupted; study drug discontinued; other).

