The investigator should exercise medical and scientific judgment in deciding whether an out of range clinical laboratory finding or finding on other assessment is clinically significant. Usually, the abnormality should be associated with a clinically evident sign or symptom, or be likely to result in an evident sign or symptom in the near term, in order to be considered clinically significant. A clinically significant laboratory abnormality in the absence of clinical symptoms may jeopardize the subject and may require intervention to prevent immediate consequences. For example, a markedly low serum glucose concentration may not be accompanied by coma or convulsions, yet be of a magnitude to require glucose administration to prevent such sequelae.

For each AE, the investigator will evaluate and report the onset (date and time), resolution (date and time), intensity, causality, action taken, serious outcome (if applicable), and whether or not it caused the subject to discontinue the study.

Pregnancy is not an AE; should a pregnancy occur, it must be recorded on a separate pregnancy form and reported as detailed below (see [Section 13.3.3](#)).

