## 14.6. Safety and Tolerability Analyses

All safety analyses will be based on the Safety analysis set. Adverse events in Study ADS-AMT-MS303 will be recorded starting immediately following completion of the last study procedure for [Study ADS-AMT-MS301](#) at a Week 16 Visit for that study (which also serves as the first visit for Study ADS-AMT-MS303). All AEs will be listed by subject and period of onset: pre-dose and TEAEs.

The incidence of TEAEs will be summarized by treatment sequences 1, 2, and 3, and overall for all subjects. The incidence of the following will be presented by system organ class (SOC) and preferred term (PT) within SOC in the safety analysis set.

- TEAEs
- Investigator-determined treatment-related TEAEs
- TEAEs leading to drug discontinuation
- TEAEs by severity

- Serious TEAEs (STEAEs)
- Investigator-determined treatment-related STEAEs
- Discontinuation due to STEAEs

Clinical laboratory test parameters will be listed for individual subjects and values outside of the reference ranges will be flagged. The incidence of potentially clinically significant changes in laboratory parameters at each study visit will be tabulated. Vital signs measurements at each timepoint will be listed by subject. The incidence of potentially clinically significant changes at each study visit will be summarized.

Descriptive statistics for the mean and mean changes in the C-SSRS will be generated by study visit. Results will also be graphically depicted.

Descriptive statistics for the mean and mean change from ADS-AMT-MS301 Screening value in the EDSS will be generated.

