#### **14.9. Completion of the Study and Withdrawals**

Withdrawals and the reason for withdrawal will be tabulated. The number and percentage of subjects who complete the study will be summarized. The number and percentage of subjects who withdraw from the study will be tabulated by treatment sequence. Study drug discontinuations will be summarized in a similar fashion.

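### Dose reduction for adverse events is allowed after Week 12, but no action-taken category or listed table identifies it, so intolerance of 274 mg/d can be understated

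*Combined protocol and SAP*

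**What the plan says.** Section 7.4.2 of the protocol states: "After Week 12, down titration from 274 mg to 137 mg due to adverse events may be considered after consultation with the Medical Monitor".

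Section 13.1.1 lists what must be recorded for each AE, including "action taken (ie, no action taken; study drug interrupted; study drug discontinued; other". The list opens with 'ie', so it is closed, and its four entries do not include a reduced dose. Section 13.2.1 repeats the requirement without naming categories: "action taken, serious outcome (if applicable), and whether or not it caused the subject to discontinue the study". Only discontinuation from the study has its own item there.

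Section 14.6 lists seven summaries of treatment-emergent AEs (TEAEs), by sequence and overall. One is "TEAEs leading to drug discontinuation" and another covers discontinuation because of serious events. Section 14.9 covers completers, withdrawals and their reasons, and adds: "Study drug discontinuations will be summarized in a similar fashion".

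The table in Section 14.5 labels all three sequences 274 mg/d in this study. Sections 7.1, 7.3, 9.4 and 9.10 likewise describe 274 mg/d for everyone after titration, without mentioning the exception in Section 7.4.2.

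The primary objective in Section 6.1 is: "To evaluate the safety and tolerability of ADS-5102 in subjects with MS and walking impairment". Section 5 ties the main purpose to the dose; it is to "extend the evaluation of the safety and tolerability of ADS-5102, an extended-release (ER) capsule formulation of amantadine administered at 274 mg/d".

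**The concern.** In a single-arm study of long-term tolerability, how many subjects could not stay on the study dose is a central result. Dose reduction and discontinuation are alternative responses to the same problem. If one is tabulated and the other is not, each reduction that replaces a discontinuation makes the reported tolerability look better without any change in how the drug was tolerated.

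The protocol provides for the reduction, but its recording rule does not recognise it. Followed as written, the rule merges reductions with every other miscellaneous action. They could then be separated only by reading free text or other records.

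**Working it through.** **Step 1: compare the dosing option with the recording rule and the listed outputs.**

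| Action on study drug for an AE | Permitted in | Own category in 13.1.1 | Listed summary in 14.6 or 14.9 |
|---|---|---|---|
| Withheld | 7.4.2 | Yes (interrupted) | None |
| Reduced to 137 mg after Week 12 | 7.4.2 | No ('other') | None |
| Stopped | 8.5 | Yes (discontinued) | Yes |

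Of the seven TEAE summaries in Section 14.6, two depend on an action on study drug, and both concern discontinuation. The other five (all, related, by severity, serious, and related serious) do not depend on drug action.

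**Step 2: follow one subject.** A subject reduced just after Week 12 who stays on drug to Week 52 contributes as follows:
- The triggering event enters the TEAE tables, correctly.
- The subject enters no discontinuation table.
- The subject counts as a completer in Section 14.9 and stays in a sequence labelled 274 mg/d.

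Time at the lower dose can reach 52 − 12 = 40 weeks, or 40/52 = 77% of treatment. Mean daily dose:
- Reduced at Week 12: (1 × 137 + 1 × 205.5 + 10 × 274 + 40 × 137)/52 = 8562.5/52 = about 165 mg.
- Never reduced: (1 × 137 + 1 × 205.5 + 50 × 274)/52 = 14042.5/52 = about 270 mg.

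**Step 3: illustrate the size.** The plan has no figure to reproduce, because it gives no expected rate of reduction or discontinuation. All rates here are assumptions. Let d be the proportion who discontinue for an AE, and r the further proportion reduced for an AE who continue to Week 52. The listed tables show d; the proportion who discontinued or were reduced is d + r. The share missed is r/(d + r).

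| | r = 2% | r = 5% | r = 10% |
|---|---|---|---|
| d = 5% | 29% | 50% | 67% |
| d = 10% | 17% | 33% | 50% |
| d = 20% | 9% | 20% | 33% |

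Worked example: d = 10% and r = 5% give 5/(10 + 5) = 33%.

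The ceiling in Section 7.2 is about 540 subjects. With that number, r = 2%, 5% and 10% correspond to 540 × 0.02 = 11, 540 × 0.05 = 27 and 540 × 0.10 = 54 subjects. These counts are upper bounds for each assumed rate, because fewer than 540 may enrol and only those still on drug after Week 12 can be reduced.

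**The case against.** The strongest reply has four parts.

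**Deferred detail.** Section 14.5 leaves the details of all analyses to a separate SAP, whose text was not available for this review. A table of dose changes is something a protocol may leave to it. This stands as a limit: such a table cannot be ruled out. A coded, dated category would still be the direct way to support it.

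**Other records.** Section 9.2 assigns drug through an interactive response system, Section 9.5 requires dates and quantities dispensed to each subject, and Section 9.3 says: "The dispensing and administration will be recorded in a drug accountability log". Section 7.4.2 also calls for consultation with the Medical Monitor. A reader might infer that reductions go unrecorded. The documents do not support that: they can be entered as 'other' and can probably be recovered. What is missing is a distinct category and a listed summary.

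**Events still counted.** A reader might also infer that the listed tables count only discontinuations, or that AE incidence is understated. Neither follows, because five of the seven TEAE summaries do not concern discontinuation, and the triggering events appear in those that apply.

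**Legitimate grouping.** Summarising by planned sequence is a reasonable choice when the protocol permits a reduction, and Section 6.1 names the drug without a dose. The grouping need not change. But Section 5 does state the purpose at 274 mg/d, and grouping by sequence does not tell the reader how many subjects left that dose. The statements in Sections 7.1, 7.3, 9.4 and 9.10 can be read as general rules with Section 7.4.2 as the exception, so a cross-reference is enough.

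**Conclusion.** The point holds as a gap in recording and reporting on the primary objective. As written, AE-driven reductions are merged into 'other', and no listed summary shows them. A subject who could not stay on 274 mg/d but reached Week 52 on 137 mg is displayed as a completer under a 274 mg/d label.

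What can be understated is intolerance of 274 mg/d. Data before Week 12 are unaffected, because the reduction is permitted only after that week, and no effect on the efficacy results is claimed.

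The size is unknown. Over the assumed ranges (d from 5% to 20%, r from 2% to 10%), between 9% and 67% of subjects who discontinued or were reduced for an AE would be missing from the listed drug-action summaries. If reductions prove rare, the effect is small. The change should be made because it is cheap and bears on the main question, but the gap does not invalidate the study.

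**What to change.** 1. **Section 13.1.1:** add 'dose reduced', with its date, to the action-taken list.
2. **Sections 14.6 and 14.9:** tabulate TEAEs leading to dose reduction, and the number, percentage and timing of down-titrations, by sequence and overall, beside discontinuations. Add a combined count of subjects who discontinued or were dose-reduced for an AE, with each subject counted once.
3. **Sections 7.1, 7.3, 9.4 and 9.10:** reconcile the 274 mg/d statements with Section 7.4.2 by cross-reference. No dose or clinical rule is proposed.

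If data collection has already begun, entries under 'other' could be coded retrospectively from the dispensing and accountability records.

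The cost is one CRF option, a few tables, and a tolerability result that may look slightly less favourable.

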### **7.5. Criteria for Study Termination**

The sponsor reserves the right to discontinue the trial at any time; reasons will be provided if this occurs. The Principal Investigator (PI) reserves the right to discontinue participation in the study for safety or other reasons at any time in collaboration with the sponsor. The investigator should notify the institutional review board (IRB) in writing of the trial's completion or early termination and provide a copy of the notification to the sponsor.

### **7.6. Duration of Subject Participation**

Maximum duration of subject participation is up to approximately 54 weeks and will include a 52-week treatment period (including a 2-week forced up-titration and a 50-week maintenance period), and a 2-week post-treatment safety follow-up period.

### **7.7. Estimated Study Duration**

The estimated study duration is approximately 2 years, from enrollment of the first subject to the last subject's last visit.

## 8. SELECTION AND WITHDRAWAL OF SUBJECTS

### 8.1. Subject Inclusion Criteria

1. Signed a current IRB-approved informed consent form
2. Successful completion of the following in Study ADS-AMT-MS301:
  - Study drug treatment for 16 weeks
  - A Week 16 Visit
3. Willing to abstain from prohibited medications (see [Section 9.7](#))

### 8.2. Subject Exclusion Criteria

1. Based on the judgement of the investigator or Medical Monitor, participation in the study would jeopardize the safety of the subject.
2. If female, is pregnant or lactating
3. If a sexually active female, is not surgically sterile or at least 2 years post-menopausal, or does not agree to utilize a highly effective hormonal method of contraception (an IUD, or vasectomized male partner is also acceptable), in combination with a barrier method, from baseline through at least 4 weeks after the completion of study treatment. If a sexually active male, does not agree to utilize condoms from screening through at least 4 weeks after the completion of study treatment.
4. Anticipated treatment with any amantadine formulation other than ADS-5102
5. Planned participation in another interventional clinical trial

### 8.3. Subject Withdrawal Criteria

Subjects will be advised that they are free to withdraw from the study at any time. Reasons that subjects may be withdrawn from the study include the following:

- Subject discontinued study drug (see [Section 8.5](#)) and wishes to withdraw
- Subject consent is withdrawn
- Sponsor decision, after discussion with the investigator

If a subject is withdrawn from the study, all efforts will be made to complete the early termination visit that includes efficacy assessments and safety follow-up. In addition, women of childbearing potential will have a post-study pregnancy test performed at the early termination visit.

All information, including the reason for withdrawal, should be reported on the applicable pages of the case report form (CRF).

For subjects who are lost to follow-up, three documented attempts will be made to contact the subject for follow-up information, including reason for discontinuation and follow-up of AEs.

Subjects who withdraw from the study will not be replaced.

## **8.4. Subject Enrollment**

All subjects must sign and date an IRB-approved informed consent form (ICF) before any study procedures, including screening procedures, are performed. Subjects will be considered enrolled into the study after they have signed the ICF and have met all study-mandated inclusion/exclusion criteria.

## **8.5. Discontinuation of Study Drug**

Subjects should discontinue study drug if judged necessary by the investigator or sponsor, and reasons may include any of the following:

- eGFR falls below 60 mL/min/1.73 m^2, confirmed by repeat testing
- Need to take a medication that is excluded or that may interfere with study measurements
  - Subjects requiring MS treatment adjustment due to disease exacerbation or progression should be discussed with one of the Medical Monitors
- Intolerable or unacceptable AEs
- Positive pregnancy test

Subjects who discontinue study drug will be withdrawn from the study, and will have an early termination visit that includes efficacy assessments and safety follow-up (see [Section 12.8](#)).

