### 5.1. Walking Impairment in Multiple Sclerosis

Adamas is developing ADS-5102, an extended-release (ER) capsule formulation of amantadine hydrochloride (HCl), as a treatment to improve walking in patients with multiple sclerosis (MS). MS is a chronic, usually progressive, autoimmune-mediated disorder of the central nervous system (CNS). The prevalence of MS in the United States (US), based on recently reported analyses of healthcare databases, is on the order of 400,000 to 675,000 individuals (Dilokthornsakul et al., 2016; Wallin, 2017). Patients generally become symptomatic early in adulthood and continue to accumulate disability throughout most of their lives. The autoimmune assault in MS can involve any part of the CNS, and by definition, affects multiple regions over time (Schumacher, 1950; Kantarci and Wingerchuk, 2006). This feature of MS makes neurological functions that depend on the integration of multiple CNS systems particularly susceptible to disability. Walking, which depends on the coordinated functioning of multiple CNS motor and sensory systems, is frequently impaired in MS. About 50% of MS patients become dependent on some form of walking aid after 15 years with the disease (Kantarci and Wingerchuk, 2006).

While there are now numerous drugs approved to reduce inflammation, and slow the progression of disability in MS, there are limited options available for the treatment of frequent, and often persistent, neurological deficits, with only one drug, dalfampridine (4-aminopyridine [4-AP]; Ampyra®) currently approved to treat walking impairment. Dalfampridine was approved in 2010 as a treatment to improve walking in patients with MS, as demonstrated by an increase in walking speed. However, this product appears to benefit only a subset of patients, comprising some 30%-60% (Goodman et al., 2009; Goodman et al., 2010; Prugger and Berger, 2013; Ruck et al., 2014 Korsen et al., 2016) of those who try it. Consequently, there remains an unmet medical need for additional therapies to treat impaired mobility in MS patients.

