## 9.8. Concomitant Medications

Information regarding medications taken by the subject throughout the study will be collected and recorded on the Prior/Concomitant Medications CRF. This information will include the name of the medication, dosage information (including frequency and route of administration), dates taken, reason for use, and stop date, if available.

As a general rule, any new medication initiated during the course of the study should be to treat an AE. Hence, the start date of a new concomitant medication should always coincide with a date of an AE, including an MS exacerbation or worsening of MS. Changes to existing, or initiation of new, MS medications (including disease modifying and symptomatic) should only be made after Week 12. If new MS medications are initiated during study participation, please inform the Medical Monitor in a timely manner.

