### 14.4. Efficacy Endpoints

Endpoints will be derived using the Week 0 assessments as the baseline value. These endpoints will consist of the changes from Baseline/Week 0 at Weeks 12, 24, and 52 in the:

- T25FW (ft/sec) and also T25FW (sec)
- TUG (sec)
- 2MWT
- MSWS-12
- The proportion of Novel Responders at each study visit, where a Novel Responder is defined as a subject who has a  $\geq 20\%$  increase from Baseline/Week 0 to the study visit in walking speed measured using the T25FW. Subjects who fail to have an increase of at least 20% at the given study visit in the T25FW (ft/sec) (non-responders) or who discontinue the study prior to this visit will be included in the denominators.

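### Sections 8.5 and 9.8 overlap without a criterion when a subject starts a new walking-related MS drug after Week 12, and the Week 24 and 52 analyses would credit that drug's effect to ADS-5102

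*Combined protocol and SAP*

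**What the plan says.** **Stopping drug.** Section 8.5 opens with discretion: "Subjects should discontinue study drug if judged necessary by the investigator or sponsor, and reasons may include any of the following". One listed reason is "Need to take a medication that is excluded or that may interfere with study measurements". Being excluded and being liable to interfere are separate limbs, so the second reaches drugs outside the prohibited list. A sub-item adds: "Subjects requiring MS treatment adjustment due to disease exacerbation or progression should be discussed with one of the Medical Monitors". The stated consequence of stopping is "Subjects who discontinue study drug will be withdrawn from the study". Section 8.3 is looser: its matching withdrawal reason is a subject who has stopped drug "and wishes to withdraw".

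**Adding MS drugs.** Section 9.8 says that changes to existing drugs, or "initiation of new, MS medications (including disease modifying and symptomatic) should only be made after Week 12". If a new one is begun, the Medical Monitor is to be told. Neither stopping study drug nor withdrawal is mentioned. Section 9.7 prohibits only other amantadine and live attenuated influenza vaccine.

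**A drug that falls under both.** Section 5.1 says: "Dalfampridine was approved in 2010 as a treatment to improve walking in patients with MS, as demonstrated by an increase in walking speed". Walking speed is what the T25FW endpoint measures.

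**Scoring.** In Section 14.4, "a Novel Responder is defined as a subject who has a" gain of at least 20% in T25FW speed over Week 0 at the visit, with no condition on other medication. Subjects who discontinue before the visit stay in the denominator. Section 14.5 reports Novel Responders, Non-Responders and discontinuations as separate categories, and gives no rule for T25FW values recorded after a new MS drug.

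**The concern.** A subject who starts dalfampridine at, say, Week 16 fits both provisions. One investigator may judge that the drug interferes with the walking tests and stop study drug. Another may rely on Section 9.8, inform the Medical Monitor and keep the subject in. The protocol expects about 80 sites and gives no criterion, so the choice may differ between like subjects.

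The choice decides the subject's category at later visits, whether later T25FW values enter the MMRM, and whether the subject can supply the Week 52 data needed for the per-protocol set. If the subject stays, the gain from the added drug is counted as a gain on ADS-5102, and a single-arm study has no concurrent untreated group against which to separate the two.

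The timing makes this matter. Week 52 T25FW is the first secondary objective, and Section 5 names durability of effect as an aim. Under Section 9.8 the new drugs can enter only after Week 12, so Week 12 is clean while Weeks 24 and 52 are exposed. That pattern could be misread as lasting or late-emerging benefit.

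**Working it through.** **1. The same event under each section.**

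| Subject starts a symptomatic walking drug after Week 12 | If study drug is stopped and the subject withdrawn (8.5) | If the subject is kept (9.8) |
|---|---|---|
| Medical Monitor | Discussion, where the cause is exacerbation or progression | Informed |
| Category at later visits (14.4, 14.5) | Discontinuation, in the denominator | Novel Responder if speed is at least 20% above Week 0; otherwise Non-Responder |
| Later T25FW values in the MMRM | Absent, not imputed | Included |

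**2. What can be reproduced.** Nothing. The protocol gives no power, alpha or effect size, and 540 is a ceiling on rollover subjects. The figures below show scale only.

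**3. Inputs.**
- Share starting such a drug after Week 12, *s*: not in the documents; assumed 5%, 10% or 15%.
- Share of starters reaching the 20% threshold, *r*: assumed 30% to 60%. This borrows the range that Section 5.1 gives for patients who benefit from dalfampridine; that section does not define benefit as a 20% gain.
- Starters are assumed not to reach the threshold without the added drug.
- Sequence size: 540/3 = 180, assuming equal sequences.

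**4. Shift in the responder proportion** between keeping all starters and withdrawing all of them: shift = *s* × *r*.

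| *s* | Starters of 180 | Reclassified at *r* = 30% | Shift (points) | Reclassified at *r* = 60% | Shift (points) |
|---|---|---|---|---|---|
| 5% | 9 | 2.7 | 1.5 | 5.4 | 3.0 |
| 10% | 18 | 5.4 | 3.0 | 10.8 | 6.0 |
| 15% | 27 | 8.1 | 4.5 | 16.2 | 9.0 |

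**5. Against sampling error.** SE = √(*p*(1−*p*)/180).
- At *p* = 8/27 = 29.6%, the Phase 2 proportion with a 20% gain (Section 5.2): SE = 3.40 points. The shift is 1.5/3.40 = 0.44 to 9.0/3.40 = 2.65 SE.
- At an assumed *p* = 10%: SE = 2.24 points. The shift is 0.67 to 4.02 SE.

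The ratio depends heavily on the base rate, and neither rate is known for this study, so the point shift is the safer statement.

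**6. Direction of error in the range.** Section 9.8 expects a new medication to treat an adverse event, including MS exacerbation or worsening. Such subjects may have slowed first and would have to recover and then pass Week 0 by 20%. The upper values of *r* are therefore probably too high for them.

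**The case against.** The strongest reply is that the two sections can be read together. Section 8.5 is discretionary and refers some MS treatment adjustments to a Medical Monitor; Section 9.8 is the specific provision for MS drugs. Keeping a subject after that discussion complies with both. This stands. A reader might infer that Section 8.5 obliges every such subject to stop while Section 9.8 lets them continue. The text does not support that: stopping is a judgement, and Section 8.3 ties withdrawal to the subject's wish. What remains is an overlap with no criterion for deciding.

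A reader might also infer that the only outcomes are discontinuation or Novel Responder. A retained subject below 20% is a Non-Responder.

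A third tempting inference is that the distortion is largest in sequence 3, whose Week 0 value was already taken on 274 mg/d. Added-drug gains there could look like late benefit, but the arithmetic gives the same point shift in every sequence, and the documents give no start rates by sequence.

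Sections 14.3 and 14.5 defer missing data and analysis details to the SAP, and the text available for review contains no such rule. A SAP could settle the classification, but it cannot reconcile Section 8.5 with Section 9.8. The per-protocol set is only a partial safeguard: it removes major deviations, and a drug that Section 9.8 permits is not clearly one.

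Finally, efficacy is secondary and there is no powered test. That limits the damage to how the responder and durability results are interpreted.

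**Conclusion.** The point holds as an unresolved overlap with a consequence for the analysis. Like subjects can be placed in different categories, and the plan as written attributes gains from an added walking drug to ADS-5102 at Weeks 24 and 52. The size is unknown. Under the assumed start and threshold rates, the responder proportion shifts by 1.5 to 9.0 points, likely an upper range. No effect on mean T25FW speed can be estimated from the documents. A claim that the shift is several standard errors would rest on an unsourced base rate and is not supported. The point does not depend on these figures. It should be corrected because it bears on the visits that carry the durability aim and the remedy is cheap.

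**What to change.** **Protocol.** Reconcile Sections 8.3, 8.5, 9.7 and 9.8 so that one rule applies when a subject needs a new or changed MS medication that can affect the walking tests. The clinical choice is the sponsor's.

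**Analysis.** Keep the Section 14.4 definition for the main analysis. Pre-specify:

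(a) a list of MS medications that can affect walking tests, fixed before database lock;

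(b) a supplementary Novel Responder analysis at Weeks 24 and 52 in which subjects who have started or changed a listed medication are not counted as responders but stay in the denominator, with their number shown by sequence;

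(c) a supplementary T25FW MMRM excluding values after that start or change.

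Item (b) should stay supplementary because it also reclassifies a subject who was already 20% faster at Week 12, and so may err downwards. Item (c) treats the excluded values as missing at random, which is doubtful if starters had worsened. Together the two show how far the main result depends on added drugs.

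**Cost.** Wording changes, agreement on the list, and a little more analysis work. The supplementary responder rate may be lower. No new data are needed, because medication names and dates are already recorded on the concomitant-medication CRF.
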